Statistical And Analytic Plan	Aim 1: Primary Endpoint (fMRI) : Only patients who completed at least two therapy sessions will participate in post-treatment assessments. We will compare fMRI activation in regions of interest at pre- and post-treatment. The design is a 2 (BATA vs MBCT) X 2 (CN, rACC) X 2 (pretreatment vs post-treatment) ANCOVA testing the change from pre- to post-treatment as moderated by treatment group and brain region in the outcome variables. Aim 2: Secondary Endpoint : To evaluate the efficacy of BATA, relative to MBCT, for treating anhedonia, we will test for differential change over time between those who receive BATA and those who receive MBCT post-treatment. We will use an intent-to-treat (ITT) analysis for patients who receive BATA relative to those who don't. The ITT model will be a repeated-measures ANCOVA with effects for treatment condition (BATA, MBCT), outcome measure (SHAPS), time (pre-treatment, post- treatment) and their interactions. The interaction tests will assess mean differences at each time point as well as differences in the degree of change between the groups. This also provides tests of each group relative to their baseline scores. We will include gender and age as covariates in these models.
DATA AND SAFETY MONITORING PLAN	We will have an independent Data Safety Monitoring Board (DSMB) that will meet twice per year to review any adverse events as well as participant accrual and adherence/drop-outs. The members of the DSMB will be responsible for safeguarding the interests of study participants, assessing the safety of all study procedures, and monitoring the overall conduct of the study. This committee will serve as an independent advisory group to the study investigators and will provide recommendations about starting, continuing, and stopping the study.

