4.2 Intervention/Treatment procedures (by visits)

BATA and MBCT Groups:

	Screening Day -14 to -1	Enrollment/Baseline Visit 1, Day 1	Study Visit 2 Day 7 +/-7 days (therapy session #1)	Study Visit 3 Day 14 +/-7 days (therapy session #1)	Study Visit 4 Day 21 +/-7 days (therapy session #2)	Study Visit 5 Day 28 +/-7 days (therapy session #3)	Study Visit 6 Day 35 +/-7 days (therapy session #4)	Study Visit 7 Day 42 +/-7 days (therapy session #5)	Study Visit 8 Day 49 +/-7 days (therapy session #6)	Study Visit 9 Day 56 +/-7 days (therapy session #7)	Study Visit 10 Day 63 +/-7 days (therapy session #8)	Study Visit 11 Day 70 +/-7 days (therapy session #9)	Study Visit 12 Day 78 +/-7 days (therapy session #10)	Study Visit 13 Day 85 +/-7 days (therapy session #11)	Study Visit 14 Day 92 +/-7 days (therapy session #12)	Study Visit 15 Day 99 +/-7 days (therapy session #13)	Study Visit 16 Day 106 +/-7 days (therapy session #14)	Study Visit 17 Day 113 +/-7 days (therapy session #15)	Study Visit 18 Day 114 +/-14 days	Final Study Visit 19 Day 115 +/-14 days
Procedures																				
Informed consent and baseline symptom measures	X																			
fMRI scan (includes urine pregnancy test and fMRI safety screen)		X						X				X								X
Randomization		X																		
Administer study intervention			X	X	X	X	X	X	X	X	X	X	X	X	X	X	X	X	X	
SHAPS		X							X			X							X	X

Questionnaires and safety assessments:

- 1) Columbia-Suicide Severity Rating Scale (C-SSRS) completed if a subject endorses suicidal thoughts at therapy visits.
- 2) 7T safety screening completed immediately before each scan.
- 3) SHAPS completed at pre-treatment, week 8, week 12, and immediately post-treatment.

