4.8 Screen failure procedures

If more than 4 weeks elapse between the baseline screen and the first scan session, this will be considered a screen fail and the individual will not be randomized.

5 STUDY EVALUATIONS AND MEASUREMENTS (how measurements will be made)

1) fMRI data (primary endpoint) will be collected at the UNC Biomedical Research Imaging Center (BRIC) at week 0, week 8, week 12, and week 15. Analyses of fMRI target engagement will focus on activation in the right CN during reward anticipation, the rACC during reward outcomes, and bilateral amygdala in response to threat. Data will be preprocessed using FSL (Oxford University, UK). We will ensure groups do not differ in head motion by calculating mean framewise displacement which yields, for each participant, a value indicating mean head displacement from one volume to the next. Hypotheses will be evaluated with a ROI approach whereby signal intensities are extracted from ROIs for the relevant task contrasts (i.e., potential win versus non-win trials during MID reward anticipation trials; wins versus non-wins during MID reward outcome trials; fearful and angry faces > shapes during the threat task). ROI analyses will be followed-up with whole-brain analyses that will yield activation maps thresholded at a False Discovery Rate of 0.01 to allow for an examination of activation in other reward processing regions, including the ventral striatum/nucleus accumbens, putamen, ventral tegmental area, and orbitofrontal cortex. To optimize BOLD signal coverage in the ventral

tegmental area we will acquire high-resolution T1-weighted images with 1x1x1 mm voxel size to allow for precise registration and will use cardiac and respiratory gated imaging during the acquisition of structural scans to address pulsatile artifacts using retrospective corrections implemented with the FSL PNM toolbox.

2) The Snaith–Hamilton Pleasure Scale (SHAPS) is a measure of anhedonia used to verify inclusion criteria. It is a well-validated 14-item self-report questionnaire that is administered by computer.

3) DSM diagnoses will be made using the SCID5, a semi-structured patient interview, and will be used to verify inclusion criteria

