5.3 Safety Evaluations

- 1) 7T MRI safety screening form
- 2) Pregnancy tests prior to each fMRI for women of childbearing potential
- 3) Columbia-Suicide Severity Rating Scale (C-SSRS), administered if the subject expresses any suicidality or thoughts that are concerning to the therapist.
- 4) If a participant reports any significant distress or refusal during the diagnostic interview session, he or she will be withdrawn immediately. If a participant reports any significant distress or refusal during the brain imaging session, he or she will be withdrawn immediately.
- 5) If a participant reveals information that they did not reveal during the screen that prevents them from participating (e.g., metallic device), or if tests positive for urine pregnancy screen, if female, they will be withdrawn from the study.

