6.4 Statistical Methods

Aim 1, fMRI outcomes: Only patients who complete at least two therapy sessions will participate in post-treatment assessments. We will compare fMRI activation in regions of interest at pre- and post-treatment. The design is a 2 (BATA vs MBCT) X 2 (CN, rACC) X 2 (pretreatment vs post-treatment) ANCOVA testing the change from pre- to post-treatment as moderated by treatment group and brain region in the outcome variables. The Treatment × Time interaction beta will be used to evaluate whether BATA produces changes in neural responses to reward anticipation and reward outcomes that exceed our *a priori* target engagement criteria (increased right caudate nucleus (CN) activation during reward anticipation and decreased rostral anterior

cingulate cortex (rACC) activation during reward outcomes) and exceed changes due to MBCT. *Post-hoc* comparisons will compare change across each region.

Aim 2, anhedonia outcomes: To evaluate the effects of BATA, relative to MBCT, for on anhedonia symptoms treating anhedonia, we will test for differential change over time between those who receive BATA and those who receive MBCT post-treatment. We will use an intent-to-treat (ITT) analysis for patients who receive BATA relative to those who don't. The ITT model will be a repeated-measures ANCOVA with effects for treatment condition (BATA, MBCT), outcome measure (SHAPS), time (pre-treatment, post-treatment) and their interactions. The interaction tests will assess mean differences at each time point as well as differences in the degree of change between the groups. This also provides tests of each group relative to their baseline scores. We will include gender and age as covariates in these models.

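### The Aim 2 SHAPS model uses only the pre- and post-treatment scores: the scheduled week 8 and week 12 scores go unanalysed, and no method is given for missing post-treatment scores (cheap improvement, secondary endpoint)

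*Combined protocol and SAP*

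**What the plan says.** Section 6.4 (Aim 2), and the synopsis in near-identical words, plan this model: "The ITT model will be a repeated-measures ANCOVA with effects for treatment condition (BATA, MBCT), outcome measure (SHAPS), time (pre-treatment, post-treatment"). The interaction is to test, among other things, "differences in the degree of change between the groups", with gender and age as covariates. The analysis is labelled intent-to-treat: "We will use an intent-to-treat (ITT) analysis for patients who receive BATA relative to those who" do not.

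The SHAPS schedule in section 4.2 has four time points: "SHAPS completed at pre-treatment, week 8, week 12, and immediately post-treatment". Section 5 describes the scale as a "14-item self-report questionnaire that is administered by computer", so it needs no scanner.

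On incomplete follow-up:
- Section 4.7 defines a dropout as three consecutive missed appointments and says that the definition enters the analyses, but not how.
- The Aim 1 paragraph of section 6.4 opens with "Only patients who complete at least two therapy sessions will participate in post-treatment assessments", and the synopsis has the same sentence.
- Section 1.3 excuses participants for suicidality or marked worsening, and section 4.5 makes new psychotropic use exclusionary.
- Section 5.3 removes participants for scan-related reasons, for example "or if tests positive for urine pregnancy screen, if female, they will be withdrawn from the study".

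No section names a method, an assumption or a sensitivity analysis for missing SHAPS scores.

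**The concern.** Treatment lasts about 15 weeks, and several routes out of the study open after randomisation. Someone who leaves after week 8 will often have a week 8 SHAPS score and no post-treatment score. A two-time model cannot use that interim score, although it may predict both the leaving and the missing outcome. The term repeated-measures ANCOVA does not settle the treatment of such participants: a complete-case fit drops them, and a likelihood fit of the two times keeps only their baseline.

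If loss differs between arms and is related to how participants are doing, the BATA versus MBCT contrast rests on a set shaped after randomisation. If loss is equal and of the same kind in both arms, only precision suffers.

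**Working it through.** **Reading check.** The model has two times and the schedule has four. The synopsis (Study Design) gives a dose purpose for the interim scans, and nothing gives a purpose for the interim SHAPS scores. Section 6.5 covers power for fMRI only, so there is no Aim 2 figure to reproduce.

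**Inputs.** From the synopsis: 60 randomised, half to each arm, so 30 per arm. Assumed: SHAPS SD of 1 at each visit, normal scores, no true effect. Loss occurs after week 8, at 30% in one arm and 10% in the other, and is logistic in the week 8 score with slope 1 (moderate) or 2 (strong) per SD. Let a be the correlation of week 8 with post-treatment, b of baseline with week 8, and c of baseline with post-treatment.

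**Step 1: bias when the week 8 score drives loss.** Let m be the mean week 8 score among those retained, measured from the full-arm mean.
- Slope 1: m = −0.253 (30% loss) and −0.091 (10% loss); difference D = 0.162.
- Slope 2: m = −0.375 and −0.143; D = 0.232.

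Absolute bias in the arm difference in change:
- complete-case change: (a − b) × D;
- pre/post likelihood fit: about (a − b·c) × D, since baseline is known for all;
- likelihood fit that includes week 8: 0, because loss depends only on a score in the model.

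| a, b, c | Slope | Complete case | Pre/post likelihood |
|---|---|---|---|
| 0.7, 0.7, 0.7 | 1 | 0 × 0.162 = 0 | 0.21 × 0.162 = 0.034 |
| 0.7, 0.5, 0.5 | 1 | 0.2 × 0.162 = 0.032 | 0.45 × 0.162 = 0.073 |
| 0.7, 0.5, 0.5 | 2 | 0.2 × 0.232 = 0.046 | 0.45 × 0.232 = 0.104 |
| 0.7, 0.3, 0.5 | 2 | 0.4 × 0.232 = 0.093 | 0.55 × 0.232 = 0.128 |

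These give the ranges of about 0 to 0.09 SD and 0.03 to 0.13 SD. They illustrate and do not bound: with a, b, c = 0.7, 0.3, 0.3 and slope 2, the pre/post figure is 0.61 × 0.232 = 0.142.

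A simulation of the third row (30 per arm, 8,000 runs; week 12 correlated 0.8 with week 8 and with post-treatment) gave bias of 0.043 (complete case), 0.107 (pre/post likelihood) and 0.003 (four-visit likelihood). Type I error was 5.3%, 6.6% and 5.0%.

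**Step 2: precision at equal loss.** In the same simulation, baseline correlated 0.5 with every later visit, and post-treatment correlated 0.5 to 0.7 with week 8 and 0.5 to 0.8 with week 12. Loss was 10% or 20%, either early (baseline only) or later (baseline and week 8 only).
- Variance of the four-visit fit relative to complete case: 0.976 down to 0.899, a saving of about 2% to 10%.
- Relative to the pre/post likelihood fit: 1.000 for early loss and 0.992 down to 0.945 for later loss, a saving of 0% to 6%.

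**Step 3: loss that no observed score predicts.** Suppose that those lost are 1 SD worse than completers, with 30% versus 10% loss and a change-score SD of 1.
- Bias = (0.30 − 0.10) × 1 = 0.20 SD. SE = √(1/21 + 1/27) = 0.291. Type I error = Φ(−1.96 + 0.20/0.291) + Φ(−1.96 − 0.20/0.291) = 10.6%.
- If post-treatment SHAPS is recovered from half of those lost, the bias left in an arm with loss p is p − (p/2)/(1 − p/2). That is 0.30 − 0.15/0.85 = 0.124 and 0.10 − 0.05/0.95 = 0.047, a difference of 0.076 SD. SE = √(1/25.5 + 1/28.5) = 0.273, and type I error is 5.9%.

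The four-visit model does not correct this kind of loss.

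**The case against.** The strongest reply is that a pre/post contrast is a legitimate choice and that no large bias is shown. Both parts stand. Complete-case bias is zero whenever the week 8 score correlates equally with baseline and with post-treatment. In a separate large-sample simulation with a true difference of 0.5 SD and about 21% to 27% loss, the complete-case and four-visit estimates were both about 0.50, and a pre/post likelihood fit gave 0.47 to 0.48. The largest harm, in step 3, assumes loss that the proposed model does not repair. The four-visit model also estimates more from 60 participants: 4 × 5/2 = 10 covariance parameters against 2 × 3/2 = 3.

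The reply does not remove the two omissions. The missing-data method is unstated, and the interim scores are collected but unused.

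Two stronger readings are tempting, and the documents do not support them:
- A reader might infer that Aim 2 is analysed by treatment received, because the intent-to-treat sentence speaks of those who receive BATA. The synopsis uses the same verb for assignment when it describes randomisation, and the model factor is treatment condition. All 60 by assigned arm is the natural reading.
- A reader might infer that post-treatment SHAPS is withheld from anyone with fewer than two sessions. The sentence "Only patients who completed at least two therapy sessions will participate in post-treatment assessments" stands in the fMRI text, and scans are its natural subject. Its wording is not limited to scans, so it needs clearing up, but it is no proof that SHAPS is withheld.

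**Conclusion.** The point holds as a cheap improvement to a secondary analysis. A concrete better method exists, uses scores that are already scheduled, and keeps the same post-treatment contrast. Under assumed 30% versus 10% loss driven by the week 8 score, it removes an absolute bias of about 0 to 0.09 SD (complete case) or 0.03 to 0.13 SD (pre/post likelihood). At equal loss it saves about 2% to 10% or 0% to 6% of the variance.

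These sizes rest wholly on assumed correlations, loss rates and loss mechanisms. The direction of any bias cannot be known from the documents. They do not show that the planned analysis is invalid, that loss will differ between arms, or that the Aim 2 result will be materially wrong. Aim 1 makes no intent-to-treat claim and is outside this point.

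**What to change.** 1. In section 6.4 and the synopsis, make the Aim 2 analysis a likelihood-based repeated-measures model (arm by visit, unstructured covariance, age and gender). Fit it to baseline, week 8, week 12 and post-treatment SHAPS for all randomised participants by assigned arm. The estimate is the post-treatment arm difference in change. Keep the pre/post analysis as supportive, and say how it treats missing scores.
2. Optionally, add a sensitivity analysis that gives worse values to missing post-treatment scores, for example by 0.5 and 1.0 SD.
3. Tidy the wording: say whether the two-session sentence covers SHAPS, and how the section 4.7 dropout definition enters the analysis.
4. Reconcile sections 1.3, 4.5 and 5.3 with the intent-to-treat claim, by stating whether SHAPS is still collected after a participant is excused or withdrawn. No clinical rule is proposed here.

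The cost is document wording, slightly more analysis work and more covariance parameters. If the reconciled text provides for SHAPS after withdrawal, a few computer-administered questionnaires are added. No extra scans are needed.

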6.5 Sample Size and Power

Power Analyses: In this study we will enroll 60 participants, whom will receive BATA treatment MBCT treatment. Based on our pilot data demonstrating increased right CN activation during reward anticipation and decreased rACC activation during reward outcomes, we calculated an effect size of approximately $z=4.1$. Conservatively, we estimate the effect size for the increased right CN activation and reduced rACC activation will be in the range of $z = (0.75-1.25)$. Our models thus have >90% power at $\alpha=0.025$.

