Test Article(s) (If Applicable)	
Behavioral Activation Treatment for Anhedonia (BATA): We have modified Behavioral Activation Treatment for Depression to create Behavioral Activation Treatment for Anhedonia (BATA) which we will evaluate in this study by comparing its effects on brain functioning relative to treatment with Mindfulness-Based Cognitive Therapy (MBCT).

Study Design	Following a phone/online screen and an initial assessment session to confirm eligibility, participants will complete a baseline fMRI session at the UNC Biomedical Research Imaging Center (BRIC). They then will be randomized to receive a 15-week course of BATA (50%) or a 15-week course of Mindfulness Based Cognitive Therapy (MBCT) (50%) administered at Duke University Medical Center (DUMC). Both groups will receive pre- and post-treatment scans as well as two mid-treatment scans (weeks 8 and 12) to evaluate treatment BATA dose.
---------------------	--

Subject Population	Inclusion Criteria
key criteria for Inclusion and Exclusion:	
 1. 18-50 years old and treatment seeking; 2. SHAPS scores ≥ 20, corresponding to clinically significant anhedonia; 3. Clinician's Global Impression Scale-Severity score (CGI-S) ≥ 3 to assure a clinically impaired sample; 4. Seeking treatment for anhedonia (i.e., referred from an outpatient clinic or responded to an advertisement for anhedonia treatment; endorses desire for treatment during screening).

Exclusion Criteria

5. Those for whom medication management is the primary gold-standard treatment, including those with bipolar disorder/mania, schizophrenia spectrum, and other psychotic disorders;
6. Prior treatment with behavioral activation therapy for depression or mindfulness-based treatments (those with exposure to other forms of psychotherapy, e.g., supportive therapy, will be eligible);
7. Those who may have difficulty understanding the cognitive components of BATA, including those with intellectual disability, neurocognitive disorders, and dissociative disorders;
8. Feeding and eating disorders which may have confounding effects on the BOLD fMRI signal;
9. Substance Use Disorders given confounding effects of substances of abuse on the BOLD fMRI signal;
10. Suicidal intent and plan;

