11. Psychotropic medication use in the past 4 weeks (8 weeks for fluoxetine) and/or current psychotherapy. Participants must be medication-free at study entry; study personnel will not supervise medication taper for the purpose of the study, but those who taper under the supervision of their regular provider will be eligible;
12. Currently pregnant, as measured by urine pregnancy screen immediately before MRI scans;
13. Positive urinalysis screen for cocaine, marijuana, opiates, methadone, amphetamines, and benzodiazepines (conducted on-site via Biosite Triage Meter Plus) at study entry.
14. No neurological conditions (e.g., history of stroke, seizure, or TBI);
15. Contraindications for 7T imaging (criteria are more stringent than for 3T imaging): Metal in the body, dental work that is not fillings or gold, any tattoos, any metal in the body, any metal injury – especially those to the eyes, any other type of implant unless they are 100% plastic.

Number Of Subjects	60 subjects will be randomized such that half will receive BATA and half will receive MBCT.
---------------------------	---

Study Duration	Approximately 16 weeks
Study Phases	(1) Phone/online Screening : initial screening for eligibility.
Screening	(2) In-Person Screening : further screening for eligibility and consent
Study Treatment	(3) Baseline fMRI
Follow-Up	(4) Initiate up to approximately 15 weeks of therapy (experimental treatment (BATA) or comparison treatment (MBCT)) (5) Mid-treatment fMRI scans at approximately weeks 8 and 12. (6) Post-treatment fMRI scan.
Efficacy Evaluations	(1) fMRI activation in right CN during reward anticipation and rACC during reward outcomes (2) Anhedonia severity (SHAPS scores)
Pharmacokinetic Evaluations	N/A
Safety Evaluations	1) 7T MRI safety screening form completed before each scan session 2) Columbia-Suicide Severity Rating Scale (C-SSRS) completed if a subject endorses suicidal thoughts at therapy visits.

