1.3 Non-Clinical and Clinical Study Findings

Potential Risks

BATA: BATA works with cognitions and emotions, some of which are distressing and difficult; they include a variety of exercises, which can be uncomfortable. It is possible that some participants receiving BATA may get worse, novel symptoms may emerge. Rd reviews have concluded that between 3% and 10% of psychotherapy clients get worse with treatment.

MBCT: MBCT works with cognitions, emotions, and sensations, some of which are distressing and difficult; they include a variety of exercises, which can be uncomfortable; and they place the formal practice of meditation at their core. It is possible that some participants receiving MBCT may get worse. A few studies have shown worsening symptoms in MBCT; however, meta-analyses consistently report significant benefits for many outcome variables in a wide range of samples. The few reviews including data on AEs and SAEs in evidence-based mindfulness practices report that they have occurred in zero to 10.6% of participants, are no more common in than in comparison conditions, and are not clinically significant.

Symptom / Behavioral Measurements: There are minimal risks involved in the collection of symptom and behavioral data. It is unlikely, but possible, that subjects may become frustrated by completing the tasks; and/or distressed at recollecting or reporting on difficult emotional experiences.

MRI: Study participants will participate in MRI scans that they would not have otherwise. The risks in this study associated with MRI scanning are comparable to having a routine MRI exam like that performed in hospitals throughout the world. There are no known risks associated with the use of MRI *per se*, but there are two areas of concern. The first is the safety risk posed by the attraction of ferromagnetic metal objects by high strength magnetic fields. The second is the discomfort some participants encounter by the confinement within the bore of the MRI system. Both types of risks occur for all clinical MRI exams and are not increased by the proposed research.

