Pregnancy: Although MRI poses no known risks to fetuses, pregnant woman will be excluded from participation according to UNC IRB policy that requires that all female research subjects of childbearing potential be given a urine pregnancy test immediately prior to the MRI scan session to rule out pregnancy.

Protections Against Risk

Symptom / Behavioral Measurements: To minimize the risk of a participant becoming stressed, the laboratory space will be designed to be patient-friendly. Breaks will be provided as requested, and assessors will be flexible in the pace and scheduling of assessments.

Treatment/Suicidality. Care will be taken to assure that no participant will be in danger of harming themselves. Any participant who reports suicidal intent will be immediately assessed using the Suicide Risk Assessment protocol. Based on the level of assessed risk, patients may be escorted to the Emergency Room for further evaluation. Participants who report a significant increase in psychiatric symptoms including suicidality will be

excused from the research protocol and referred for more extensive treatment, including referral for medications, if desired. Following the conclusion of the trial, all participants will be provided with referral information as appropriate for further treatment.

MRI: This MRI studies follow guidelines with regard to specific absorption ratio (SAR) and limits on gradient slew rate (dB/dt). Participants will be interviewed and will fill out a screening questionnaire for 7T imaging safety prior to entering the MRI suite. Participants will be instructed to remove all metal objects, including clothing with metal clasps, before entering the magnet room. Some participants may feel uncomfortable or confined once positioned within the MRI system. This potential reaction will be reduced by discussing the procedure prior to entry, by providing the participant with a mirror through which they can look out into the room, and by communicating with the participant over the intercom.

Confidentiality: To protect confidentiality, only alphanumeric ID numbers, rather than names, will appear on clinically sensitive charts and digital data. The key linking the alphanumeric identifier and participant's identity will be maintained on a separate drive that will be double password protected and to which only the PIs and key study personnel will have access. All research personnel will have completed HIPPA training for researchers and CITI training.

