4.7 Subject Completion/ Withdrawal procedures

Completion: Participants will complete the study after 15 weekly treatment sessions.

Withdrawal procedures. Patients may opt to discontinue participation at any time. Any patient who misses three consecutive scheduled appointments will be a dropout, and this will be explained to patients during consent and whenever a patient begins missing sessions. This operational definition of dropout will be used in data analyses.

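### Section 6.5 claims more than 90% power on all 60 enrolled with no allowance for lost scan pairs, and for the Treatment × Time contrast the claim is not met across the plan's own effect range

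*Combined protocol and SAP*

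**What the plan says.** Section 6.5 (Sample Size and Power) gives a single sample size: "In this study we will enroll 60 participants, whom will receive BATA treatment MBCT treatment". It cites a pilot effect of z = 4.1, takes 0.75 to 1.25 as a conservative range, and concludes that power exceeds 90% at alpha 0.025. It does not say what z measures, which test the power refers to, or whether the test is one- or two-sided.

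The synopsis (Number Of Subjects) shows that 60 is the number randomised, not a target of evaluable patients: "60 subjects will be randomized such that half will receive BATA and half will receive MBCT". Under Study Design, randomisation follows the baseline scan, so later losses are post-randomisation losses.

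Section 6.4 bases Aim 1 on pre- and post-treatment activation and on the Treatment × Time interaction. The week 8 and week 12 scans are not in that model. The intent-to-treat statement is made for Aim 2 only, and no method for a missing post-treatment scan is given for Aim 1.

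These rules can remove the second scan:
- Section 6.4: "Only patients who complete at least two therapy sessions will participate in post-treatment assessments".
- Section 1.3: certain C-SSRS answers lead to excusal from the trial. Also, "Participants who report a significant increase in psychiatric symptoms including suicidality will be" excused from the research protocol.
- Section 4.5: psychotropic medication started during the study is exclusionary.
- Section 5.3: distress or refusal at a scan, a positive pregnancy screen, or a newly revealed contraindication leads to withdrawal.

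Section 4.7 defines a dropout as a patient who misses three consecutive appointments and adds: "This operational definition of dropout will be used in data analyses". No dropout rate, evaluable N or replacement rule appears anywhere.

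**The concern.** Only a patient with both scans supplies a change score for the primary contrast. The plan lists several routes by which the second scan can be lost and defines dropout for use in analysis, yet the power paragraph allows for no loss over 15 weekly sessions and four 7T scans. It also gives one figure for a range of effects, without saying where in that range the figure applies.

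This is the primary endpoint. A null Treatment × Time result would be judged against a claim of more than 90% power, and would look more conclusive than it is if the true power were nearer 60 or 70%.

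**Working it through.** **Inputs.** From 6.5: N = 60, effects 0.75 to 1.25, alpha 0.025. From the synopsis: 1:1 allocation, 30 per arm. From 6.4: the contrast is the between-arm difference in pre-to-post change. Assumed, because the documents are silent: the effect is a standardised between-arm difference in change, d; each region is tested by a t test; losses are equal in the two arms; the loss is 0, 10, 20 or 30%, that is 60, 54, 48 or 42 pairs.

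**Formula, between arms.** Noncentrality λ = d·√(n₁n₂/(n₁+n₂)), df = N − 2; power is the probability that a noncentral t exceeds its critical value. For d = 0.75 and N = 60: λ = 0.75·√15 = 2.905, with critical value 2.301 two-sided or 2.002 one-sided. Power is 72.6% or 81.5%.

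**Step 1: can the plan's figure be reproduced at N = 60?** It depends on the reading.
- Between-arm d: yes at 1.0 (93.9% two-sided) and at 1.25 (99.4%); no at 0.75 (72.6%; 81.5% one-sided).
- Paired test within BATA, 30 pairs, λ = 0.75·√30 = 4.108: yes, 95.4% two-sided and 97.8% one-sided. This is not the Treatment × Time contrast.
- Between-arm effect of 0.75 on the raw activation scale: yes, if the pre/post correlation is high enough. With a correlation of 0.7 and change scores, 0.75/√(2 × 0.3) = 0.968 and power is 92.3% two-sided. With 0.6 and ANCOVA, 0.75/√(1 − 0.36) = 0.9375 and power is 90.5%. The plan states no correlation.

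**Step 2: loss of pairs, between-arm contrast.** Two-sided power, one-sided in brackets:

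| Pairs | d = 0.75 | d = 1.0 | d = 1.25 | Smallest d with 90% power |
|---|---|---|---|---|
| 60 | 72.6% (81.5%) | 93.9% (96.8%) | 99.4% (99.7%) | 0.930 (0.851) |
| 54 | 67.3% (77.2%) | 91.0% (95.0%) | 98.7% (99.5%) | 0.983 (0.899) |
| 48 | 61.2% (72.0%) | 87.0% (92.4%) | 97.5% (98.9%) | 1.046 (0.956) |
| 42 | 54.5% (66.0%) | 81.5% (88.5%) | 95.4% (97.7%) | 1.123 (1.025) |

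At d = 1.0 two-sided, power is 89.8% with 52 pairs, so the claim fails once 8 of 60 (13%) are lost.

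**Step 3: loss of pairs, within-BATA test at 0.75** (λ = 0.75·√n, df = n − 1):

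| BATA pairs | Two-sided | One-sided |
|---|---|---|
| 30 | 95.4% | 97.8% |
| 27 | 92.8% | 96.3% |
| 24 | 89.0% | 94.0% |
| 21 | 83.5% | 90.5% |

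**Reading the tables.** A 10% loss takes none of the tabulated cases from above 90% to below it; two-sided, it matters only for d between about 0.93 and 0.98. A 20% loss does so on the two-sided readings (87.0% between arms at 1.0; 89.0% within BATA at 0.75) but not on the one-sided ones (92.4% and 94.0%). At 0.75 between arms the claim already fails with all 60 pairs; attrition makes it worse but does not cause it.

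**The case against.** The best defence is that z is undefined and sidedness is unstated, while the Aim 1 hypotheses in 6.1 and 6.4 are directional. On a one-sided within-BATA reading, more than 90% holds across the whole effect range even after a 30% loss. That stands: 6.5 cannot be called arithmetically wrong under every reading. But 6.4 names the Treatment × Time interaction as the test, and a within-arm figure does not describe its power.

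A reader might infer that attrition alone defeats the power claim. The documents do not support that, for three reasons.

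- **No documented rate.** Section 1.3 says that "between 3% and 10% of psychotherapy clients get worse with treatment". Taken as the loss, this would leave 54 to 58 of 60. But getting worse, with no threshold, is not the same event as the significant increase in symptoms that leads to excusal. Ten per cent is at most an upper figure for that one route, if everyone who worsens is excused. Losses of 20 or 30% are assumptions.
- **Treatment dropout is not scan loss.** Section 4.7 defines a dropout but does not say that dropouts go unscanned. The two-session threshold in 6.4 can be read as keeping later dropouts in the post-treatment assessment.
- **Effect size matters more.** At 1.25 the claim survives every loss considered; at 0.75 between arms it fails with no loss at all.

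It is also fair to say that the attrition figures cannot be written into 6.5 until metric, test and sidedness are settled, so the two repairs belong together.

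**Conclusion.** The point holds in limited form. Section 6.5 ties its power to 60 enrolled, all of whom are randomised, and makes no allowance for missing scan pairs although the plan's own rules can produce them. That fewer than 60 pairs will remain is a well-founded expectation, not a documented count.

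For the Treatment × Time contrast, the claim is not delivered across the stated range: with 54 to 60 pairs, an effect of 0.75 has 67 to 73% power two-sided or 77 to 82% one-sided. At 1.0 it holds at 10% loss and, at 20%, depends on sidedness. At 1.25 it holds throughout. These figures assume that z is a standardised between-arm difference in change, that losses are equal by arm, and that each region is tested separately at alpha 0.025. It would go too far to say that the trial lacks its stated power because of dropout.

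**What to change.** Keep 60 randomised and rewrite the paragraph in 6.5 to:
1. define the effect metric (including the pre/post correlation if the effect is on the raw scale), the test and the sidedness;
2. state an assumed loss of pre/post scan pairs, labelled as an assumption;
3. replace the single power claim by the power for the Treatment × Time contrast at 0.75, 1.0 and 1.25 for 60, 54 and 48 pairs; or by the smallest effect with 90% power at those numbers, which on the reading used here is 0.93, 0.98 and 1.05 two-sided, or 0.85, 0.90 and 0.96 one-sided.

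The cost is one paragraph and a less favourable stated power. No additional patients, scans or procedures are needed.
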